4.8.12. Subgroup Analyses

Subgroup analyses of PFS and OS will be performed for potential prognostic subgroup variables, including but not limited to

- All baseline stratification factors
- *ESR1* mutation status (mutation detected versus mutation not detected), for the analyses comparing Arm A versus Arm B and Arm C versus Arm A in the ITT population
- Measurable disease at baseline (yes versus no)
- Bone only disease at baseline (yes versus no)
- Age (<65 years versus \geq 65 years)
- Region (North America, Europe, Asia, and Other)
- Race (Caucasian, Asian, and Other)
- Progesterone receptor status (positive versus negative)
- Baseline ECOG PS (0 versus 1)
- Number of sites involved (1 versus 2 versus 3+).
- Intended use of endocrine therapy in the control arm (fulvestrant versus exemestane)
- Endocrine resistance (primary versus secondary)
- Prior CDK4/6 inhibitor (yes versus no)
 - If yes, setting (adjuvant versus metastatic)
 - If yes and received prior CDK4/6 inhibitor in the metastatic setting, length of the prior CDK4/6 inhibitor (≥ 12 months versus <12 months)
- Type of prior CDK4/6 inhibitor (palbociclib versus ribociclib versus abemaciclib versus dalpiciclib)
- HER2 status (low [IHC 1+ and IHC 2+] versus negative [IHC=0])
- Prior therapy history, for example, subgroup variables derived per inclusion criteria 3a-c in the protocol if deemed appropriate
 - o patient progressing while on or within 12 months of adjuvant treatment (see 3a),
 - patient progressing more than 12 months after completion of (neo)adjuvant treatment with subsequent progression on or after only 1 line of therapy (see 3b),
 - patient presenting metastatic disease de novo with subsequent progression on or after only 1 line of therapy (see 3c)

If a level of a factor consists of fewer than 5% of total number of events, analysis within that level may be omitted. The level of "missing/unknown" may be dropped if deemed appropriate. Other subgroup analyses may be performed as deemed appropriate. A forest plot will be used to present the results graphically. P-values for the interaction between the treatment and subgroup variables will be reported.

Subgroup analyses may also be performed for safety analyses (such as for summary of TEAE), including but not limited to age group, gender, race, region, menopausal status and baseline *ESR1* mutation status.

Subgroup analyses for Japan and China regulatory submissions will be described in a separate SAP addendum.

4.8.13. Biomarker Analyses

Biomarkers related to treatment, mechanism of action, and/or cancer will be measured and analyzed. The association of biomarker and clinical outcome will be assessed via single-marker and/or multi-marker analysis. Baseline *ESR1* mutation status (mutation detected versus mutation not detected) will be summarized. Baseline is defined as pre-treatment sample collected on the first date of dose (C1D1) when available. If the C1D1 pre-treatment sample fails or is not provided or not sufficient plasma is provided, the screening sample will be used as baseline.

4.8.14. Important Protocol Deviations

Important protocol deviations that potentially compromise the data integrity and participants' safety will be summarized. These deviations will include deviations that can be identified programmatically and those which can only be identified by the clinical research associates during monitoring. Important protocol deviations are described in another document within the study Trial Master File.

4.9. Interim Analyses

4.9.1. Data Monitoring Committee

Interim analyses for safety and efficacy will be conducted under the guidance of an independent data monitoring committee (DMC). The DMC will consist of at least 3 members, including 2 clinicians and 1 statistician. The DMC will communicate any recommendations based on interim analysis to the Sponsor senior management designee (SMD). If necessary, the SMD may form an internal review committee (IRC) to review and act upon the recommendations of the DMC. Details will be provided in a separate DMC charter.

4.9.2. Safety Interim Analyses

The DMC will monitor the overall safety of the study. An early safety analysis will be performed after approximately 100 participants have been randomized and had the opportunity to be treated for 1 cycle. The DMC will meet and review data approximately every 6 months thereafter. At the recommendation of the DMC, the frequency of safety interim analyses may be modified.

At each interim analysis, the DMC may recommend the trial continue without modifications, continue with specific modifications, or be stopped for safety concerns. There will be no prespecified rules for stopping the trial due to safety concerns. The DMC members will review unblinded safety data at each interim analysis. If a significant safety signal is identified, the DMC may recommend a protocol amendment, termination of enrollment, and/or termination of study treatment. The recommendations of the DMC will be communicated to the Sponsor SMD.

In the event that safety monitoring uncovers an issue that needs to be addressed by unblinding at the treatment group level, members of the DMC can conduct additional analyses of the safety data. Additionally, unblinding of a limited number of the Sponsor representatives external to the study team may be required for evaluation of selected SAEs for determination of regulatory reporting.

4.9.3. Efficacy Interim Analyses

One interim analysis is planned for the primary endpoint of PFS between Arm A and Arm B, when approximately 192 of the 480 events (40% information fractions, respectively) have been observed in the analysis population as defined in Section 3. The purpose of this interim is to allow the trial to stop early due to futility. The beta-spending function is used to control the type II error rate, which is determined by the gamma family. The DMC should recommend stopping the trial (for the comparison between Arm A versus Arm B) for futility if the hazard ratio is above 1.128. The boundary will be updated based on the actual number of observed events. There is no intent to declare statistical significance for superior efficacy at this interim; therefore, there is no impact on the statistical significance levels for the final analysis.

Table 4.4.Stopping Boundaries for Each Analysis Between Arm A and Arm B in the ITT
Population Based on the Initial Allocation of Alpha for Illustration

Analysis	Number of	Information Fraction	Critical P-value	Critical Hazard	Cumulative Type I	Boundary Crossing Probabilities ^a		sing a
	Events		Boundary	Ratio	Error Rate	Hazard	Hazard	Hazard
				Boundary		Ratio =	Ratio =	Ratio =
						0.74	1	1.25
Interim 1	192	40%	NA	1.128	NA	0.002	0.203	0.757
Final	480	1009/	0.005	0.790	0.005	0.759	0.005	0
FINAL	i 480	100%	(efficacy)					

Abbreviations: ITT = intention-to-treat; NA = not applicable.

^a Boundary crossing probabilities under different hazard ratio assumptions.

For PFS between Arm A and Arm B in the *ESR1*-mutation detected population, if approximately 192 events have been observed in this subset at the time of final PFS analysis in the ITT population, the final PFS analysis for the *ESR1*-mutation detected population will be conducted at the 1-sided alpha level of 0.02 (assuming the initial alpha level based on the graphical approach). If the target number of events in this subset has not been reached at this time, 1 interim analysis for efficacy may be conducted in the subset at this time if deemed appropriate. The Lan-DeMets spending function (O'Brien-Fleming type) will be used to determine the boundaries at the interim and final analyses for PFS in the *ESR1*-mutation detected population. In this situation, DMC will review the final analysis in the ITT population and be instructed to recommend to the SMD that the results for the comparison between Arm A and Arm B be released to the Sponsor if PFS in the ITT population is statistically significant based on the initial alpha. If the number of events in the subset is close enough to the target number of events (e.g., at least 180 events have been observed assuming a target number of 192 events) then the final analysis for PFS in the subset may be performed at this time.

Table 4.5 summarizes the boundaries for PFS in the *ESR1*-mutation detected population assuming 1 interim look will be performed, with the look 1 at approximately 180 events. The boundaries will be updated based on the actual number of observed events and the actual 1-sided alpha level that is used for this endpoint per the graphical approach.

0.727

0.733

0.016

0.020

Illustration (Assuming 1 Interim Look)							
		Critical	Critical	Cumulative			
Number of	Information	P-value	Hazard Ratio	Type I Error			
Events ^a	Fraction	Boundary	Boundary	Rate			
	Number of Events ^a	on (Assuming 1 Interim Loo Number of Information Events ^a Fraction	Detected 1 optimition based on the initial An on (Assuming 1 Interim Look)Number of EventsaInformation FractionP-value Boundary	on (Assuming 1 Interim Look) Number of Information P-value Hazard Ratio Events ^a Fraction Boundary Boundary			

0.016 (efficacy)

0.016 (efficacy)

Table 4.5.Stopping Boundaries for Each Analysis Between Arm A and Arm B in the ESR1-
mutation Detected Population Based on the Initial Allocation of Alpha for
Illustration (Assuming 1 Interim Look)

Abbreviation: ITT = intention-to-treat.

180

192

Look 1 (at final in ITT)

Final

^a Number of events at Look 1 was estimated based on enrollment and PFS assumptions and assuming that the sample size of *ESR1*-mutation detected subset is approximately 240 patients.

94%

100%

One interim analysis is planned for the primary endpoint of PFS between Arm C and Arm A after approximately 100 of the 248 events (40% information fraction) have been observed in the analysis population for this comparison as defined in Section 3. The purpose of the interim is to allow the trial comparison for Arm C versus Arm A to stop early (stop the enrollment to Arm C if not completed) due to futility. The beta-spending function is determined by the gamma family. The DMC should recommend stopping the trial (for Arm C versus Arm A) for futility if the hazard ratio is above 1.126. The boundary will be updated based on the actual number of observed events. There is no intent to declare statistical significance for superior efficacy at this interim; therefore, there is no impact on the statistical significance levels for the final analysis. The study will continue after the interim analysis if the futility interim is passed.

Table 4.6.Stopping Boundaries for Each Analysis between Arm C and Arm A in the ITT
Population Based on the 1-sided Alpha Level of 0.025 for Illustration

			Critical	Critical	Cumulative	Boundary Crossing Probabilit		obabilities ^a
	Number	Information	P-value	Hazard Ratio	Type I	Hazard	Hazard	Hazard
Analysis	of Events	Fraction	Boundary	Boundary	Error Rate	Ratio = 0.7	Ratio = 1	Ratio = 1.25
Interim	100	40%	NA	1.126	NA	0.009	0.279	0.705
Final	248	100%	0.025	0.779	0.025	0.794	0.027	0
			(efficacy)					

Abbreviations: ITT = intention-to-treat; NA = not applicable.

^a Boundary crossing probabilities under different hazard ratio assumptions.

Only the DMC is authorized to evaluate unblinded safety and efficacy interim analyses. Study sites will receive information about interim results only if they need to know for the safety of their participants.

An interim analysis may be collapsed with any other analyses including a final analysis if they are expected to occur within a similar timeframe (e.g., within approximately 2 months).

Additionally, the final analysis of PFS between Arm A and Arm B in the ITT population may be collapsed with the final analysis in the *ESR1*-mutation detected population or the final analysis between Arm C and Arm A in the ITT population if they are expected to occur within a similar timeframe. At the time of the final evaluation of PFS between Arm A and Arm B in the ITT population or in the *ESR1*-mutation detected population, whichever is later (if they are not collapsed), the Sponsor will only have access to Arm A and Arm B data and will be blinded to

Arm C if the final analysis between Arm A and Arm B is before the final analysis between Arm C and Arm A.

Unblinding details are specified in a separate blinding and unblinding plan document.

5. Sample Size Determination

Participants will be randomly assigned to Arm A, Arm B or Arm C in a 1:1:1 ratio until the target enrollment for arms A and B (a total number of approximately 640 participants) is reached.

Though Arm C was added to the study (amendment a) after first patient visit for Arms A and B, all arms will be closed at the same time. Randomization of patients will continue in Arms A and B (1:1) until amendment (a) is approved and implemented, at which point patients will be randomized 1:1:1 (A:B:C) until the target enrollment is met.

To adjust for multiplicity and control the overall type I error rate at 0.025 (1-sided), the graphical approach (Bretz et al. 2009; Mauer and Bretz 2013) will be used to test the 3 PFS hypotheses and the 3 OS hypotheses. Initially, the overall 1-sided alpha level of 0.025 will be split between PFS for Arm A versus Arm B in the ITT population (H₁) and PFS for Arm A versus Arm B in the *ESR1*-mutation detected population (H₂), with H₁ tested at the 1-sided alpha level of 0.005 and H₂ tested at the 1-sided alpha level of 0.02. Zero alpha is initially assigned to the PFS endpoint for Arm C versus Arm A in the ITT population (H₃) and OS endpoints. Details are described in Section 4.3.3.

As the overall alpha is initially split between H_1 and H_2 , the study will be considered positive (for Arm A versus Arm B) if either PFS in the ITT population (H₁) or PFS in the *ESR1*-mutation detected population (H₂) is statistically significant. The power and associated sample sizes for H₁ and H₂ are based on the initial allocation of alpha. The analysis population for the first primary hypothesis (PFS for Arm A versus Arm B in the ITT population) is all participants randomized to Arm A and Arm B. The primary analysis of PFS for Arm A versus Arm B in the ITT population will be performed after approximately 480 investigator-assessed events have been observed (that is, a 25% censoring rate) in Arm A and Arm B. Assuming a PFS hazard ratio of 0.74, a total of 480 events yields at least 76% power to detect superiority of imlunestrant Arm A over Arm B with the 1-sided log-rank test at the significance level of 0.005. If H1 can be tested at the full alpha level of 0.025 after recycling per the graphical approach (Figure 4.4), the same number of events can yield at least 91% power with the 1-sided log-rank test. The median PFS of Arm B is assumed to be 4.3 months, and the hazard ratio of 0.74 amounts to an approximate 1.5-month improvement in median PFS under the assumption of exponential survival distribution. The assumed median PFS of Arm B is estimated based on an unpublished metaanalysis of historical controls.

The analysis population for the second primary hypothesis (PFS for Arm A versus Arm B in the *ESR1*-mutation detected population) is the *ESR1*-mutation detected subset in Arm A and Arm B. The primary analysis of PFS will be performed after approximately 192 investigator-assessed events have been observed in the *ESR1*-mutation detected subset. Assuming a PFS hazard ratio of 0.57, a total of 192 events yields approximately 97% power to detect superiority of Arm A over Arm B with the 1-sided log-rank test at the significance level of 0.02. Assuming the median PFS of Arm B in the subset is 3.6 months, the hazard ratio of 0.57 amounts to an approximate 2.7-month improvement in median PFS under the assumption of exponential survival distribution.

The power and sample size for H_3 is based on the 1-sided alpha level of 0.025 assuming that both H_1 and H_2 are rejected. The analysis population of the third primary hypothesis (PFS for Arm C

versus Arm A in the ITT population) is the participants concurrently randomized to Arm A and Arm C. The primary analysis of PFS will be performed after approximately 248 investigatorassessed events have been observed in this analysis population. Assuming a PFS hazard ratio of 0.7, a total of 248 events yields at least 80% power to detect superiority of Arm C over Arm A with the 1-sided log-rank test at the significance level of 0.025. If the median PFS of Arm A is assumed to be 5.8 months (assuming the target HR for Arm A versus Arm B in the ITT population is met), the hazard ratio of 0.7 then amounts to an approximate 2.5-month improvement in median PFS under the assumption of exponential survival distribution. Per the enrollment assumptions below, it is estimated that 220 participants will be enrolled in Arm C. Thus approximately 440 participants will be concurrently randomized to Arm A and Arm C.

The following enrollment assumptions are considered to estimate the planned total sample size for this study.

- 1. Participants will be enrolled at a rate of 5, 10, 15, 20, 25, 35, 35, 35, 35, 35, 40, 40, 40, 40/month for the first 14 months, and at a rate of 45/month for the reminder of the enrollment period.
- 2. Arm C will enter the study 6 months after the first patient visit.
- 3. Once arm C enters, participants will be randomly assigned to 1 of the 3 arms at a gradually increasing rate until the peak, specifically, at a rate of 15, 15, 18, 18, 36, 36, 36, 36/month for 8 months, and 45/month thereafter.
- 4. After Arm C is added to the trial, participants may continue to be randomized to arms A and B (at the sites where Arm C is not fully implemented yet), at a monthly rate which is the difference between the rates in assumption 1 and those in assumption 3 in the corresponding months, until amendment a (Arm C) is implemented at all sites.
- 5. All arms will be closed at the same time.

Under these assumptions, it is estimated that a total number of 860 participants will be enrolled to this study. Specifically, approximately 320 participants will be enrolled in Arms A and B respectively, and approximately 220 participants in Arm C.

The sample size calculation is conducted in EAST version 6.5.

6. Supporting Documentation

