ESR1-mutation detected population. PFS for Arm C versus Arm A in the ITT population will be inferentially tested only if the PFS for Arm A versus Arm B in either the ITT population or the *ESR1*-mutation detected population is statistically significant. Further details are provided in Section 9.

- The primary analysis of PFS between Arm A and Arm B in the ITT population will be performed after approximately 480 investigator-assessed PFS events have been observed in Arm A and Arm B.
- The primary analysis of PFS between Arm A and Arm B in the *ESR1*-mutation detected population will be performed after approximately 192 investigator-assessed PFS events have been observed in the *ESR1*-mutation detected subset (or 80% of the participants in this subset have experienced an event, whichever is earlier) in Arm A and Arm B.
- The primary analysis of PFS between Arm C and Arm A will be performed after approximately 248 investigator-assessed PFS events have been observed among the participants concurrently randomized to Arm A and Arm C.

Under the enrollment assumptions, it is estimated that a total of approximately 860 participants (320 in Arm A, 320 in Arm B, and 220 in Arm C) will be enrolled to this study. Details on sample size determination (including the enrollment assumptions) and statistical considerations are described in Section 9.

Please refer to Section 1.2 for a study schema.

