6.3. Measures to Minimize Bias: Randomization and Blinding

This is a randomized, open-label study. The route of administration for the anti-cancer agents in the study justifies an open-label design. Upon obtaining informed consent, site personnel should

access the IWRS, which will assign a patient number. Participants who meet all criteria for enrollment will be randomly assigned to the treatment arm. Assignment to treatment groups will be determined by a computer-generated random sequence using the IWRS. Sites will be prompted to enter the specific Arm B ET of choice at time of randomization until the enrollment to Arm B is stopped. Each participant in this study will be aware of his or her own assigned treatment group. At each investigative site, all staff involved in treating and caring for study participants will have full knowledge of treatment assignments for the participants under their care.

In order to maintain the scientific integrity of the trial, access to study data will be strictly controlled prior to the interim and final analyses. Access to the EDC will be limited to those who require this information for their role and all access will be documented.

For the accumulated aggregate database to which Sponsor statisticians (or those of its designee) have access, treatment assignment, and other parameters that can disclose treatment assignment will be scrambled or masked. Therefore, the Sponsor and all investigative sites will remain blinded to treatment group assignments for the aggregate database until the database lock for the final analysis. Scrambled treatment assignments will be used in the reporting database until the study reaches its final analysis or the study is determined to be positive or futile by the DMC. During this time, analyses using unblinded treatment codes will be performed only at the interim analysis points specified in the protocol/SAP.

Participants will be randomized 1:1:1 between the 3 treatment arms, of either imlunestrant (Arm A), Investigator's Choice Endocrine Therapy (Arm B), or imlunestrant plus abemaciclib (Arm C), using the following stratification factors:

- previous treatment with any CDK4/6 inhibitor (yes versus no)
- presence of visceral metastases (yes versus no); visceral includes lung, liver, brain, pleural, and peritoneal involvement, and
- region (East Asia versus North America/Western Europe versus Others).

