Figure 4.2b. Graphical representation of testing scheme when H2 is rejected for illustration. Small edge weights are represented by dotted lines. Edge weights are rounded off to 4 decimal places.

Figure 4.2c. Graphical representation of testing scheme when both H1 and H2 are rejected for illustration. Small edge weights are represented by dotted lines. Edge weights are rounded off to 4 decimal places.

Taking H₁ as an example, H₁ is initially tested based on the allocated 1-sided local significance level of $\alpha = 0.005$ from the initial α -split. If H₁ cannot be rejected at this significance level, it can be re-tested based on a higher significance level of $\alpha = 0.019$ if H₂ is rejected based on the initially allocated 1-sided local significance of $\alpha = 0.02$ (Figure 4.2b). If H₁ cannot still be rejected, it can be re-tested again at an even higher 1-sided local significance level of $\alpha =$ 0.02499645 if both H₂ and H₃ are rejected (Figure 4.4). Similarly, if H₂ cannot be rejected based on the allocated initial 1-sided local significance level of $\alpha = 0.02$, it can be re-tested again at a higher 1-sided local significance level of $\alpha = 0.0249989$ if both H₁ and H₃ are rejected (Figure 4.3). As H₁, H₂ and H₃ are all event-driven, their final analyses may occur at different times (e.g., the hypotheses can be tested in the following order: first H₁, then H₂ and finally H₃). If re-testing of any hypotheses needs to occur at a later timepoint, the p-value associated with the original test statistic (observed at the prespecified final analysis for the corresponding hypothesis) will be compared against the updated local significance level. The analysis based on longer follow-up (after the final analysis) will not serve as basis for inferential testing.

Figure 4.3. Graphical representation of testing scheme when both H₁ and H₃ are rejected for illustration. Small edge weights are represented by dotted lines. Edge weights are rounded off to 4 decimal places.

Figure 4.4. Graphical representation of testing scheme when both H₂ and H₃ are rejected for illustration. Small edge weights are represented by dotted lines. Edge weights are rounded off to 4 decimal places.

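### Does SAP 4.9.3 leave the DMC without a release rule if the ESR1-mutation result crosses its boundary before the ITT result is significant?

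*SAP*

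**What the plan says.** SAP 4.9.3 covers the case where the ESR1-mutation detected subset has not reached its target when the ITT final PFS analysis falls due. In that case, "1 interim analysis for efficacy may be conducted in the subset at this time if deemed appropriate", with Lan-DeMets O'Brien-Fleming boundaries. Table 4.5 illustrates this with a look at 180 of 192 events, nominal p 0.016, HR 0.727. The DMC then reviews the ITT final analysis and recommends that A versus B results be "released to the Sponsor if PFS in the ITT population is statistically significant based on the initial alpha". The initial alpha is 0.005 for H1 and 0.02 for H2 (SAP 4.3.3 and 5). The next sentence allows the H2 final analysis to be done at that time if the subset is close to target, with 180 of 192 as the example.

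Other parts of the plan bear on the point:

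- SAP 5: "the study will be considered positive (for Arm A versus Arm B) if either PFS in the ITT population" or PFS in the subset is significant.
- SAP 4.3.3: if H1 fails at 0.005, "it can be re-tested based on a higher significance level of" 0.019 once H2 is rejected, using the p-value from H1's own final analysis.
- Protocol 6.3: treatment codes stay scrambled until the final analysis or until "the study is determined to be positive or futile by the DMC".
- Protocol 4.1: the H2 analysis is triggered at 192 events or when "80% of the participants in this subset have experienced an event, whichever is earlier".
- SAP 4.9.3, on timing: "An interim analysis may be collapsed with any other analyses including a final analysis if they are expected to occur within a similar timeframe", with about 2 months as the example.
- SAP 4.9.3, on access: "Unblinding details are specified in a separate blinding and unblinding plan document". SAP 4.9.1 defers DMC details to a charter. Neither document is available here.

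**The concern.** Amendment (d) moved most of the alpha to the ESR1-mutation subset because external data suggested that the benefit sits there. H2 is therefore the likelier route to a positive trial, yet the one written release trigger rests on H1 at 0.005. A DMC that saw H2 cross with an ITT p-value of 0.01 would have two rejections under the graph (H2, then H1 at 0.019) and no sentence in SAP 4.9.3 telling it what to recommend. A partial rule can be read as a complete one. The committee might then hold back a positive result, or settle the question after seeing unblinded data. The futility boundaries for A versus B and for C versus A each come with an explicit DMC action, which makes the silence on H2 more noticeable.

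**Working it through.** **Inputs.** ITT: 480 events, HR 0.74, one-sided alpha 0.005. Subset: target 192 events, HR 0.57, one-sided alpha 0.02, about 240 patients (footnote to Table 4.5), Arm B median 3.6 months (SAP 5). Assumptions: proportional hazards, exponential PFS, 1:1 allocation.

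**The plan's own figures reproduce.**

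- The drift of a log-rank Z with d events is −ln(HR)·√d/2. For H1 this is 0.3011·√480/2 = 3.298, and power at 0.005 is Φ(3.298 − 2.576) = 76.5% (SAP: at least 76%). For H2 with 192 events, power at 0.02 is 96.7% (SAP: about 97%).
- The spend at the look is 2(1 − Φ(z₀.₉₉/√t)). With t = 180/192 it is 0.0163, so Z = 2.138 and the HR bound is exp(−2 × 2.138/√180) = 0.727, as in Table 4.5.
- The level of 0.019 is 0.005 + 0.7 × 0.02.

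**How often the unstated case arises if the look is run.** H1 and H2 are bivariate normal with correlation √(d/480).

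| Subset events d | H2 boundary p | P(H2 crosses) | P(H2 crosses, ITT p > 0.005) | of which ITT p < 0.019 |
|---|---|---|---|---|
| 140 (assumed) | 0.0064 | 79.9% | 13.2% | 8.1 points |
| 160 (assumed) | 0.0108 | 89.6% | 17.0% | 10.0 points |
| 180 (Table 4.5) | 0.0163 | 94.9% | 19.7% | 11.3 points |

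With no effect outside the subset and d = 180, the ITT HR is exp(180·ln 0.57/480) = 0.81 and the share is 55.6%. The last column is not a second gap. H1 can be tested at 0.019 only after H2 is rejected, so those trials already sit inside the column before it.

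**Where the look would fall.** The footnote to Table 4.5 says that 180 was estimated from the enrolment and PFS assumptions. Rebuilding it from the SAP 5 accrual rates and medians, with no dropout, gives about 182 subset events when ITT reaches 480, and 192 about 1.4 months later. At that count the SAP lets the H2 final analysis go ahead, or the analyses be collapsed. H2 is then final and no interim release rule is needed.

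**Cost if the DMC waited instead.** t = −ln(1 − missing/at risk) × median/ln 2, with medians 3.6 and 3.6/0.57 = 6.3 months.

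- 12 missing of 60 at risk: 1.2 to 2.0 months.
- 12 missing of 40 at risk: 1.9 to 3.2 months.
- 32 missing of 80 at risk: 2.7 to 4.7 months. This needs 160 events in 240 patients, a 67% event rate while ITT stands at 480/640 = 75%. The plan gives the subset the shorter control median (3.6 against 4.3 months), so this case is strained.
- In a smaller subset the 80% trigger applies. With the subset at 75% when ITT is, it has 75/80 = 94% of its target, the same ratio as 180/192. If every event-free patient is still at risk, the wait is again 1.2 to 2.0 months.

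**What a DMC would infer.** Table 4.5 presents the look-1 value as a stopping boundary for efficacy. SAP 5 defines positive as H1 or H2. Protocol 6.3 ends scrambling when the DMC determines that the study is positive. Read together, an H2 crossing is a positive result that the DMC may report.

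**The case for a change.** The strongest case for a change is that the SAP chose to write a release rule here and wrote half of it. The route carrying four fifths of the alpha is the half left out. The Protocol 6.3 sentence is general text about masked codes, not an instruction for this look. The routes around the gap (H2 final analysis at about 180 events, collapsing within about 2 months) are permissions, so an interim look could still be run. Pre-specification exists so that a DMC need not interpret, and one sentence would close the matter at no alpha cost.

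Most of this stands as a description. The sentence is silent on H2, the case is not excluded, and clearer wording would be harmless. It does not show that following the plan as written goes wrong. The instruction says when to release and does not say that nothing else may trigger release. It concerns the DMC's review of the ITT final analysis, so it reads naturally as H1's rule. The missing instruction is also of the kind assigned to the charter and the unblinding plan, which may already contain it.

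**Conclusion.** No change is needed. The SAP omits a release sentence for an H2 crossing at an optional look, and a DMC can fill that gap from the rest of the plan. Type I error is unaffected, because the boundary and the graph are fully specified. No rejection is lost, because H1's original p-value is kept for re-testing. The 13% to 20% range (56% with no effect outside the subset) is conditional on the look being run as an interim and is not the chance of meeting the gap. The largest values belong to 180 events, where the plan offers two ways to avoid an interim altogether. The realistic cost is a question to the committee or a wait of about 1 to 3 months, assuming exponential PFS, a subset of about 240 and 40 to 60 patients still at risk. If the SAP is revised for another reason, the sentence could say that release follows rejection of H1 or H2 under the graphical procedure, with the charter and unblinding plan checked to match. That is optional.
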